1.0 Introduction and Background

In patients with SCD, the use of low dose anticoagulation as an outpatient may lead to a significant decrease in morbidity and as a result, decrease healthcare utilization and costs. Sickle cell disease (SCD) is most commonly affected by recurrent painful vaso-occlusive crisis (VOC) and although greater than 50% of patients with SCD have significant daily pain, only 5% of patients actually seek medical attention (Smith, 2008). Importantly, hospitalizations account for up to 90% of the medical care costs for patients with SCD (Yang, 1995). Review of data from the National Center for Health Statistics revealed the average direct costs per hospitalization (in 1996 dollars) was estimated at \$6300, for a total direct cost of \$475 million per year. The use of anticoagulation in SCD builds upon recent studies including our own (Shah, 2012; Ataga, 2007; Francis, 1989; Stuart 2001) which document a hypercoagulable state and has been found to be promising in smaller past studies.

Although few studies have attempted to evaluate clinical pain scores in the context of anticoagulation, several studies have examined the effects of anticoagulation on the coagulation system in SCD. Wolters et al documented that use of acenocoumarol at a mean INR of 1.64 resulted in a 50% decrease in plasma prothrombin fragment 1+2 in SCD patients during steady state. However, clinical evaluation was not performed in this initial small study (Wolters, 1995). Subsequently, Ahmed et al measured D-dimer in 37 sickle cell patients treated with low dose warfarin (mean dose of 1 mg) while in crisis. Their results revealed a significant decrease in D-dimer levels in patients treated with warfarin (Ahmed, 2004). These studies also documented no bleeding with low dose anticoagulation, along with the decrease in hypercoagulable markers.

Studies evaluating the clinical benefit of anticoagulation in patients with SCD began with Chaplin et al, who revealed that long term use of daily prophylactic subcutaneous heparin in four SCD patients over several years (mean 8.7 years) was beneficial. Minimal improvement in clinical pain was reported in one, and moderate improvement in three. Results also included no bleeding and no thrombocytopenia. In addition, there was a 73% reduction in days of hospitalization per year and 74% reduction in hours spent in emergency rooms per year during heparin administration. Pretreatment pain patterns recurred when heparin was discontinued (Chaplin, 1989). A larger study by Schnog et al examined 22 SCD patients in a double blind placebo controlled, cross-over pilot study. This study used acenocoumarol dosed to achieve an INR of 1.6-2 and followed patients for a total of 23 weeks. Results included reduction in all hypercoagulable markers; however, there was no decrease in the number of hospitalizations. Limitations of this study arose from the small sample size and the large number of patients excluded (Schnog, 2001). Furthermore, subcutaneous heparin and warfarin may not be the optimal antithrombotic agents to use in this particular clinical setting. Thus, the inconclusive results from previous studies indicate that further investigations are needed to more effectively evaluate the role of low dose anticoagulation in SCD.

2.0 Study Rationale

There is not only significant morbidity associated with patients with SCD, but also costs associated with the numerous hospitalizations. Small studies have been unable to show clear benefit of the use of low dose anticoagulation in SCD due to limited sample size or the inclusion of very specific populations. However, studies have shown a decrease in the level of elevated prothrombotic markers with anticoagulation, and one

Impact of Daily Prophylaxis Dose Anticoagulation with a Factor Xa Inhibitor (Apixaban) in Patients with Sickle Cell Disease

study using full dose anticoagulation in patients with a generally milder form of SCD (with high protective hemoglobin) showed more rapid decrease in clinical pain with use of anticoagulation, suggesting a possible benefit of such therapy. Due to the paucity of data to support therapeutic dose LMWH in the more severe forms of SCD seen in the United States, we are currently performing an inpatient study to evaluate if prophylactic dose LMWH not only reduces the known hypercoagulable state, but more importantly, has a salutary effect on clinical pain scores. This study proposal attempts to critically avoid admissions by reducing daily pain scores and pain crisis as an outpatient by use of a novel oral anticoagulant.

The development of novel anticoagulants such as oral direct factor Xa (FXa) inhibitors allows the realistic use of daily prophylactic dosing as an outpatient. Past studies as detailed earlier have been limited by attempts to use subcutaneous injections or frequent, close monitoring for acenocoumarol treatment, both which are not ideal for chronic daily use. Furthermore, the use of global assays such calibrated automated thrombography (CAT) have shown further details about thrombin generation in a population which is hypercoagulable at baseline. Our studies have revealed an increase in 'thrombin burst' and intrinsic hypercoagulability which can be monitored closely by CAT during treatment with a FXa inhibitor.

There is evidence of the potential role of anticoagulants for reduction in this hypercoagulable state, and importantly reduction in clinical pain. Studies of anticoagulation in outpatients with SCD have included the use of LMWH and acenocoumarol. Both have difficulty in administration, monitoring and ultimately compliance. The development of direct factor Xa (FXa) inhibitors which are administered orally and require minimal monitoring is ideal for chronic administration.

3.0 Study Design

This is a double blind, parallel group, placebo controlled feasibility study (see figure 1) with an enrollment target of 60 patients (30 per arm). All subjects that meet inclusion criteria as an outpatient, following a 1 month observation, will be randomized to receive an oral prophylactic dose factor Xa inhibitor (Apixaban 2.5mg po bid) or placebo for 6 months. Subjects will return for a 30 day (+/- 5 days) follow-up visit after the End of Treatment (EOT) visit. Initial randomization will occur by computerized randomization technique by the investigational drug services (IDS) at Duke University Medical Center.

3.1 Screening and Eligibility

All patients seen in our Adult Comprehensive Sickle Cell Center will be screened for eligibility. Currently, there are greater than 450 patients actively seen and an average of 60 patients seen per week. The same inclusion/exclusion criteria will be used for both arms of the study.

Inclusion Criteria

[figure not shown]
- documented HgbSS, SC or HgbS-beta⁰ thalassemia,
- age ≥ 18 years old and ≤ 80 , seen in outpatient clinic ≥ 2 times in past year, and
- seen for an acute care visit (hospitalization, emergency department, or day hospital visit) for pain > 2 times in the past year.

Impact of Daily Prophylaxis Dose Anticoagulation with a Factor Xa Inhibitor (Apixaban) in Patients with Sickle Cell Disease

Exclusion Criteria

- Hospitalization or day hospital visit for pain crisis within the past 2 weeks
- Patients with ≥ 10 acute care visits within the past year will be excluded
- Creatinine > 3.0 mg/dL
- creatinine ≥ 1.5 mg/dL AND **weight** ≤ 60 kg
- chronic use of antiplatelet or anticoagulation medication
- Patients with known vasculopathy or Moya-Moya
- platelet count $< 100 \times 10^9/L$
- AST or ALT > 3 times normal
- chronic red blood cell transfusions (scheduled transfusions)
- packed red blood cell transfusion within the past 2 months
- Use of CYP3A4 and P-gp inhibitor medications

4.0 Specific Aim 1. Evaluate the impact of daily prophylactic dose anticoagulation (oral direct factor Xa inhibitor) on daily pain scores in outpatients with SCD.

4.1 Study Procedures Aim 1

Following randomization by IDS, and initial blood draw (Figure 1), patients will be given a daily pain log. Patients will record daily pain scores and return in 1 month (+/- 5 days) at which time patients will then be given a 1 month supply of study drug. Patients will return monthly (+/- 5 days) to return daily pain logs, verify compliance to medication, review completion of daily pain logs, and give additional study drug for the next month. Patients must adhere to daily administration of study drug and miss no more than 2 doses per week. Clinical pain scores will also be performed with each visit. The primary pain assessment tool will be a 10-cm horizontal visual analog scale (VAS), with “0” corresponding to no pain at one end and “10” indicating the worst pain at the other. The daily pain log will include the VAS and if the patient classifies their pain as ‘crisis’ or not. Patients will be called monthly between in person visits to assess for AE/SAE and to reinforce the importance of medication compliance. Along with the VAS, there will be novel methods of pain assessment that may prove to better measure the impact of pain in these patients. One method is the use of the validated PROMIS format. PROMIS uses a 5-point Likert-type format with response options ranging from never to always. A total score is calculated by obtaining a sum of scores across items, with higher scores indicating greater impact of the particular domain to a patient’s daily living. Patients will have PRO performed on enrollment, after 1 month’s use of study drug and at the end of 6 months’ use of study drug. Patients will complete PROMIS on a mobile device and have all results

Impact of Daily Prophylaxis Dose Anticoagulation with a Factor Xa Inhibitor (Apixaban) in Patients with Sickle Cell Disease

recorded on the Duke secure server for further information. The second, a SMART application will be installed on patient's iPhones/iPads at their request to assist with monitoring of symptoms. Patients without an Apple device can have one loaned to them until completion of the study.

The devices will be returned to the study PI or coordinator per agreement at the time of enrollment. Patients admitted to the hospital will continue their study drug or placebo unless deemed medically inappropriate by admitting physician. Patients upon discharge are to resume study drug per supervision of study

principal investigator. Pain scores during hospitalization and for the subsequent 1 week will be recorded and used for secondary analysis of daily pain scores during crisis.

Patients who during the course of the study have laboratory findings which reveal creatinine ≥ 1.5 mg/dL AND weight ≤ 60 kg; platelets $< 100 \times 10^9/L$; or develop AST or ALT > 3 times normal, will have study drug stopped and will be terminated from the study.

Patients on hydroxyurea will be included in the study and sub-analysis will be performed to control for potential differences. All patients despite treatment with hydroxyurea will need to meet inclusion criteria of having clinically significant pain which requires > 2 acute care visits.

4.2 Data and Statistical Analysis Aim 1

We power the study to test whether there is a significantly larger reduction in pain after administration of a daily prophylactic anticoagulation dose as compared to administration of a placebo. A total of 60 patients will be randomly assigned to each drug arm. The primary endpoint is the mean pain score per patient over each of four time periods. The design has two sources of variation: the variation between the patients receiving the same drug and the variation due to the interaction of time by the patients within drug arm. It is of interest to test whether the change in the pain score over the four time periods differs between the prophylactic anticoagulation dose arm and the placebo arm. From the literature the standard deviation of the mean pain score per patient is 1.5. Assume the true mean pain scores over the four time periods for the placebo and prophylactic anticoagulation dose arms are 3.9, 3.9, 3.9, 3.9 and 3.9, 3.12, 3.12, 3.12, respectively. Then, a total of 60 patients randomized equally to each drug arm will detect the difference in the change between the two arms in the mean pain scores over time, as specified by the preceding mean pain scores, with a power of at least 0.836 for a one-sided 0.05 test. Anticipating that 20% (10 patients) may have incomplete data (less than 75% of daily pain scores recorded or missing more than one dose of study drug per week), may be lost to follow up, or may drop out; we have also found a power of at least 78.4% for 50 patients.

We expect two positive effects from prophylactic doses of apixaban on the patient reported outcomes:

- PROs assessing fatigue, physical function, and pain impact will improve in patients administered daily prophylactic dose apixaban compared to placebo.*
- We believe that there will be a significant correlation between PROs and pain scores.*

Statistical Analysis

The primary outcome of interest is to test the effect on the mean daily pain score due to the arm by time interaction. Secondary outcome will include comparison of daily pain scores while hospitalized between treatment arms and the number of hospitalizations during each treatment period.

Impact of Daily Prophylaxis Dose Anticoagulation with a Factor Xa Inhibitor (Apixaban) in Patients with Sickle Cell Disease

[figure not shown]
All analyses will be performed using SAS version 9 or greater (SAS Institute Inc., Cary, NC). Data will be analyzed using descriptive statistics including mean and standard deviation. Comparisons are to be performed using SAS's PROC GLM with a model that accounts for all fixed and random effects in the design.

5.0 Specific Aim 2: Determine the effect of prophylactic dose anticoagulation on markers of thrombin generation during outpatient steady state as well as inpatient VOC.

As described in section 3.0, we will perform a double blind, parallel group, placebo controlled feasibility study with an enrollment target of 60 patients (30 per arm).

5.1 Study Procedures Aim 2

As described earlier (Figure 1), patients begin a 1 month observation following randomization. Patients will have blood drawn on enrollment and when they return in 1 month (+/- 5 days) to begin study drug. Subsequent blood draws performed at 2 month intervals while on study drug. Blood draws will occur between 2 and 4 hours from previous dose taken and ± 5 days regardless of hospitalization. Patients will be called monthly between in person visits to assess for AE/SAE and to reinforce the importance of medication compliance. Graded incentives may be given monthly to encourage patients to continue on study and return for follow up blood draws.

Platelet poor plasma will be separated and stored to allow batch testing for hypercoagulable markers and markers of inflammation. Markers of thrombin generation will include D-dimer, thrombin-antithrombin (TAT) complex, and CAT. Both D-dimer and TAT will be performed using enzyme-linked immunosorbent assay (ELISA). CAT will be performed using the Fluoroskan Ascent plate reader (TCoag) and phases to be analyzed include lag phase, slope, peak and endogenous thrombin potential. Markers of inflammation will also be measured at each of these time points (IL-6 and sVCAM) which are performed by ELISA.

Patients admitted to the hospital will continue their study drug or placebo unless deemed medically inappropriate by admitting physician. Patients upon discharge are to resume study drug per supervision of study principal investigator. Blood will be drawn for secondary analysis for hypercoaguability on any inpatient hospitalizations on day 1, 3 and 5 but will not be included in primary analysis.

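### The exclusion list names no criterion for active bleeding, past major or intracranial bleeding, or a known bleeding disorder, so such patients are not barred from six months of blinded apixaban

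*Combined protocol and SAP*

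**What the plan says.** Section 3.0 describes a double-blind, placebo-controlled feasibility study of 60 patients, 30 per arm, with apixaban or placebo taken for 6 months. Section 3.1 lists 11 exclusions, the same for both arms. Among them are "chronic use of antiplatelet or anticoagulation medication", "Patients with known vasculopathy or Moya-Moya", "Creatinine > 3.0 mg/dL", "AST or ALT > 3 times normal", a platelet count below 100 x 10^9/L, and use of CYP3A4 and P-gp inhibitors. No item mentions bleeding.

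In the text available for this check, bleeding appears only in section 1.0, as background. Of the acenocoumarol and low-dose warfarin studies the plan says: "These studies also documented no bleeding with low dose anticoagulation, along with the decrease in hypercoagulable markers". Of the four-patient heparin series it says: "Results also included no bleeding and no thrombocytopenia".

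On study, section 4.1 names three triggers: creatinine at or above 1.5 mg/dL with weight at or below 60 kg, low platelets, and raised AST or ALT. Patients who meet one "will have study drug stopped and will be terminated from the study".

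**The concern.** The investigational drug is an anticoagulant, given blinded to outpatients. The list in 3.1 already bars several indirect markers of bleeding risk, yet it is silent on the direct evidence: that the patient is bleeding now, has bled seriously before, or is known to have a bleeding disorder. The two sit oddly together. Known vasculopathy excludes a patient, while a past intracranial haemorrhage without known vasculopathy does not.

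At stake is the safety of any such patient who is enrolled. A careful investigator may well decline to enrol one, but that decision would rest on unwritten judgement. It could not be verified against the protocol or applied uniformly.

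**Working it through.** The plan gives no figure on this point, so the main check is a reading of the text.

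**1. Sort the exclusions in 3.1.** The plan does not state its reasons, so the grouping is a reading.
- Bearing on bleeding risk or drug exposure (7): creatinine alone; creatinine with weight; antiplatelet or anticoagulant use; vasculopathy or Moya-Moya; platelets; AST or ALT; CYP3A4 and P-gp inhibitors.
- Other (4): recent hospital or day-hospital visit for pain; 10 or more acute care visits in a year; scheduled transfusions; red cell transfusion in the past 2 months.
- Naming active bleeding, bleeding history or a bleeding disorder: 0.

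7 + 4 = 11, so every item is accounted for.

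**2. Run a test patient through the list.** Take an adult with HgbSS, at least 2 clinic visits and 4 acute pain visits in the past year, platelets of 110 x 10^9/L, other laboratory values within limits, none of the excluded drugs, and no recent transfusion or pain admission. Four visits exceed the required 2 and fall short of the excluding 10. A count of 110 is above the limit of 100. Now add a past intracranial haemorrhage without known vasculopathy, or an inherited bleeding disorder. No criterion is triggered, and the patient is eligible.

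**3. Look for a rule elsewhere that would catch this patient.**
- 3.0 randomizes those who meet the criteria, and 3.1 contains no exclusion at the investigator's discretion.
- 6.1 requires a relevant medical history and an eligibility decision, but a bleeding history corresponds to no criterion, so the history has nothing to be judged against.
- The mandatory termination triggers in 4.1 are laboratory limits, one of them combined with weight.
- 4.1 and 5.1 let an admitting physician judge study drug medically inappropriate. This applies only once the patient is in hospital.
- 9.3.3 and 9.3.4 foresee interruption or discontinuation for adverse events and laboratory findings, without a bleeding rule.
- 9.3.7 lists liver injury as the only event of special interest, and 9.1.1 and 9.3 ask staff not to question subjects about specific events.

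**4. What 30 patients on apixaban can show about bleeding, whatever the exclusions.** If no bleed is seen, the one-sided 95% upper bound p solves (1 - p)^30 = 0.05, so p = 1 - 0.05^(1/30) = 9.5%. The documents give no bleeding rate. For assumed true 6-month risks, the chance of at least one event is 1 - (1 - p)^30:

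| Assumed risk | Chance of at least 1 event in 30 |
|---|---|
| 1% | 26.0% |
| 2% | 45.5% |
| 5% | 78.5% |
| 10% | 95.8% |

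The information on bleeding is limited mainly by sample size. One event moves the arm's observed rate by 1/30 = 3.3 percentage points, but that is true of any event in any arm of 30 and says nothing about the missing criterion.

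**The case against.** The plan is not indifferent to bleeding risk. Seven of its exclusions plausibly reduce it, and the item on vasculopathy or Moya-Moya is itself such a control. The 2-month transfusion exclusion would remove some patients with a recent serious bleed. Adverse events are assessed at each visit and call after screening, and physicians may withhold study drug in hospital. All of this stands, and it narrows the gap. It does not close it: the transfusion item reaches only bleeders who were transfused, and the other provisions act after the patient is already in the trial and are discretionary.

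A reader might infer that the trial would enrol the patients at highest bleeding risk. The documents do not support this: the text permits such patients but does nothing to select them.

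A reader might also infer that the omission undermines the safety conclusion, or could set off a recommendation by the data and safety monitoring board to stop. The primary outcomes are pain (4.2) and thrombin generation (5.2). Safety is general event collection with tabular board review (9.3), and no safety hypothesis or bleeding endpoint is stated. The same criteria apply to both randomized arms, so no between-arm bias arises. The board may recommend termination, but predicting that it would do so for this reason is conjecture.

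Nor does the rationale in 2.0 rest on absence of bleeding. The two quoted statements are background reports on earlier studies of other drugs.

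**Conclusion.** The point holds as a participant-safety gap. None of the 11 exclusions names active bleeding, previous major or intracranial bleeding, or a bleeding disorder, and no mandatory bleeding-specific rule elsewhere makes up for it. It should be corrected or justified. It does not invalidate the efficacy comparison, and there is no stated safety conclusion for it to threaten.

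Its size cannot be expressed as a number of patients or events, because the documents give neither the frequency of such histories in the clinic nor a bleeding rate. The conclusion rests on the exclusion list being complete as it appears. The text available for this check does not show the figure at the inclusion criteria or the contents of Appendix A, so it should be confirmed that neither carries a bleeding criterion.

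**What to change.** Bring 3.1 into line with the plan's own bleeding-risk exclusions by adding an explicit eligibility item on active bleeding, bleeding history and bleeding disorder, or record in the protocol why none is needed. The sponsor should set the clinical definitions and any look-back window; none is proposed here. The Investigator Brochure is cited in 9.3.2 only for safety reporting, so if it is to be the source for these definitions the protocol should say so.

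Check the item against the medical history already taken at Screening (6.1), and reconfirm it at Month 1 (6.1.3) before study drug is first dispensed, because a month passes in between. Under 6.1 the patient is already randomized by then, so the plan should also state how a patient found ineligible at that recheck is counted among the 60 and in the analysis.

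The cost is a short amendment, with no new assessment at Screening and one added question at Month 1. Some otherwise eligible patients will be lost. The number cannot be derived, but it should be small beside a clinic of more than 450.

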6.0 Study Visit Procedures (See Appendix A)

6.1 Screening/Randomization Visit

The investigator or designee will:

- Obtain written informed consent
- Obtain relevant medical history
- Determine eligibility
- Conduct pregnancy test (WOCBP only)
- Obtain blood samples for research laboratory tests
 - Research labs include: D-dimer, thrombin-antithrombin, and calibrated automated thrombography, IL-6, sVCAM
- Assess concomitant medication use

Impact of Daily Prophylaxis Dose Anticoagulation with a Factor Xa Inhibitor (Apixaban) in Patients with Sickle Cell Disease

- Randomize subject
- Perform Pain Score
- Distribute Pain log
- Perform Patient Reported Outcome Computerized Questionnaire (PROMIS)
- Install SMART app on subject's phone or provide subject with a device

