6.1.2 Observational Period (30 days)

Via a telephone contact at 2 weeks, the investigator or designee will:

- Assess concomitant medication use
- Review pain log completion guidelines
- Assess adverse events

6.1.3 Month 1

The investigator or designee will:

- Obtain blood samples for research laboratory tests
 - Research labs include: D-dimer, thrombin-antithrombin, and calibrated automated thrombography.
- Assess concomitant medication use
- Perform Pain Score
- Dispense study drug
- Assess pain log completion compliance
- Assess adverse events

6.1.4 Month 1, 2, 3, 4, 5, 6, 7 and 8 (telephone) – 2 weeks following last clinic visit

Via a telephone contact, the investigator or designee will:

- Assess concomitant medication use
- Review pain log completion guidelines
- Assess adverse events

6.1.5 Month 2

The investigator or designee will:

- Assess concomitant medication use
- Perform Pain Score
- Dispense study drug
- Assess pain log completion compliance
- Assess adverse events
- Perform Patient Reported Outcome Computerized Questionnaire (PROMIS)

6.1.6 Month 3

The investigator or designee will:

- Obtain blood samples for research laboratory tests
 - Research labs include: D-dimer, thrombin-antithrombin, and calibrated automated thrombography.
- Assess concomitant medication use
- Perform Pain Score
- Assess study drug compliance

Impact of Daily Prophylaxis Dose Anticoagulation with a Factor Xa Inhibitor (Apixaban) in Patients with Sickle Cell Disease

- Dispense study drug
- Assess pain log completion compliance
- Assess adverse events

6.1.7 Month 4

The investigator or designee will:

- Assess concomitant medication use
- Perform Pain Score
- Assess study drug compliance
- Dispense study drug
- Assess pain log completion compliance
- Assess adverse events

6.1.8 Month 5

The investigator or designee will:

- Obtain blood samples for research laboratory tests
 - Research labs include: D-dimer, thrombin-antithrombin, and calibrated automated thrombography, IL-6, and sVCAM.
- Assess concomitant medication use
- Perform Pain Score
- Assess study drug compliance
- Dispense study drug
- Assess pain log completion compliance
- Assess adverse events

6.1.9 Month 6

The investigator or designee will:

- Assess concomitant medication use
- Perform Pain Score
- Assess study drug compliance
- Dispense study drug
- Assess pain log completion compliance
- Assess adverse events

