9.3.4 Laboratory Test Abnormalities

All laboratory test results captured as part of the study should be recorded following institutional procedures. Test results that constitute SAEs should be documented and reported as such.

The following laboratory abnormalities should be documented and reported appropriately:

- any laboratory test result that is clinically significant or meets the definition of an SAE
- any laboratory abnormality that required the subject to have study drug discontinued or interrupted
- any laboratory abnormality that required the subject to receive specific corrective therapy.

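### Section 4.1 turns three of the four entry laboratory limits into mandatory stops but omits creatinine above 3.0 mg/dL, leaving participants over 60 kg with no mandatory numeric creatinine stop

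*Combined protocol and SAP*

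**What the plan says.** The exclusion list in Section 3.1 has four laboratory limits: "Creatinine > 3.0 mg/dL"; a lower creatinine limit of 1.5 mg/dL for those weighing 60 kg or less; a platelet count under 100 × 10⁹/L; and AST or ALT over three times normal.

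Section 4.1 then names the laboratory findings that end treatment. It covers participants who "have laboratory findings which reveal creatinine ≥ 1.5 mg/dL AND weight ≤ 60 kg", and it repeats the platelet and transaminase limits. The consequence is not optional: study drug is stopped and the participant is terminated from the study. Creatinine above 3.0 mg/dL is not on this list.

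Two other places bear on stopping:

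- Sections 4.1 and 5.1 have hospitalized patients continue study drug "unless deemed medically inappropriate by admitting physician".
- Section 9.3.4 asks for documentation and reporting of "any laboratory abnormality that required the subject to have study drug discontinued or interrupted".

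Neither gives a creatinine value.

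**The concern.** The authors carried the laboratory entry limits into the stopping rule unchanged, with one exception, and the text gives no reason for it. The result is uneven. A participant at or below 60 kg must stop at 1.5 mg/dL, while a heavier participant has no stated ceiling. One would expect a deliberate design to set some upper value for heavier participants, even if it differed from the entry limit.

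What is at stake is individual safety. Treatment is a double-blind anticoagulant or placebo for 6 months. Followed to the letter, the stopping sentence lets a participant over 60 kg remain on drug at a creatinine that the same protocol treats as disqualifying at entry. Stopping then rests on individual judgement, although the other three limits are mandatory. The point does not bear on the power calculation or the primary analysis.

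**Working it through.** The plan states no figure on this point, so there is nothing to reproduce. The check is a comparison of the two lists.

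**Step 1. Entry limits against stopping limits.**

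| Limit | Section 3.1: excludes at entry | Section 4.1: mandatory stop |
|---|---|---|
| Creatinine > 3.0 mg/dL, any weight | Yes | **No** |
| Creatinine ≥ 1.5 mg/dL with weight ≤ 60 kg | Yes | Yes, same threshold |
| Platelets < 100 × 10⁹/L | Yes | Yes, same threshold |
| AST or ALT > 3 times normal | Yes | Yes, same threshold |

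Three of four are carried over and one is not.

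**Step 2. Who is affected.**

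- Weight ≤ 60 kg: the stop applies from 1.5 mg/dL and so already covers every value above 3.0. The omission has no effect.
- Weight > 60 kg: the joint condition is false whatever the creatinine, so no creatinine stop exists. Entry is allowed up to and including 3.0 mg/dL, because only values above 3.0 exclude. A 61 kg participant who goes from 3.0 to 3.1 or 6.0 now fails an entry criterion but meets no stop.

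**Step 3. Whether other text closes the gap.**

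- The admitting physician's discretion applies to inpatients only, and the default is to continue.
- Section 9.3.4 governs reporting and sets no threshold.
- Section 9.3.6 requires discontinuation for pregnancy.
- Section 9.3.7 concerns liver injury.
- The safety board review in Section 9.3 works at study level.

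None supplies a creatinine value.

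**Step 4. Possible size.** The documents give neither the weight distribution nor the rate of renal decline. The following shares are assumptions, used only to show a range: 50% to 90% of participants weigh over 60 kg, and 0% to 5% of those pass 3.0 mg/dL on study.

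- All participants: 60 × 0.5 × 0 = 0, up to 60 × 0.9 × 0.05 = 2.7.
- Apixaban arm: 30 × 0.5 × 0 = 0, up to 30 × 0.9 × 0.05 = 1.35.

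**Step 5. Whether such a value would be seen.** The Section 6 lists show blood draws at five visits: Screening and Months 1, 3, 5 and 8. They name research assays, for example "Research labs include: D-dimer, thrombin-antithrombin, and calibrated automated thrombography", with IL-6 and sVCAM added at some visits. None of the five names creatinine. Drug is first dispensed at Month 1 and treatment ends at Month 7, so only the Month 3 and Month 5 draws fall on treatment. Section 6.0 refers to Appendix A, whose content is not in the text supplied, so creatinine may be scheduled there.

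**The case against.** The strongest reply accepts the comparison and disputes its weight.

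- **An entry limit need not be a stopping limit.** Nothing in the protocol says the two lists must match, and repeating three of four items suggests an oversight without proving one. This stands, and it is why the point is called a probable omission.
- **Clinical safeguards exist.** Beyond the admitting physician, resumption after discharge is supervised by the principal investigator. Abnormal laboratory findings can be adverse events, which are assessed at visits and at calls between them. Section 9.3.3 provides for follow-up of nonserious events that lead to interruption or discontinuation, and all events go to the safety board. These make it less likely that a known high value would be ignored. They remain discretionary or reporting provisions and set no creatinine limit.
- **The size is assumed.** This also stands. Only the count of three in four comes from the documents.
- **The silence on testing proves little.** The Screening list calls for eligibility to be determined yet names none of the laboratory tests that this needs, so the lists are evidently incomplete for clinical tests. Any monitoring gap would also affect the other three stops equally. Testing is therefore something to confirm and is not evidence for the omission.
- **The remedy loses data.** The sentence ends participation as well as treatment, so each added stop removes a participant from follow-up. This is a real cost, but it falls on someone who would have been ineligible at entry on the same value.

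**Conclusion.** The concern holds. Section 4.1 omits one of the four entry laboratory limits, and participants over 60 kg have no mandatory numeric creatinine stop anywhere in the text supplied. At or below 60 kg there is no gap.

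The frequency cannot be derived and may be zero; the range of 0 to 2.7 participants, with 0 to 1.35 on apixaban, rests wholly on the assumed shares. No estimate, power figure or analysis changes. The conclusion also depends on Appendix A containing no separate creatinine stop, which could not be checked.

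The change should be made because the rule, followed exactly, leaves such a participant on an anticoagulant, and the correction uses a threshold the sponsor has already chosen. Confidence is medium, since the omission may have been intended.

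**What to change.** Add creatinine above 3.0 mg/dL, at any weight, to the stopping sentence in Section 4.1 so that it matches Section 3.1. If the omission was deliberate, state the reason, or give a different on-study limit for participants over 60 kg.

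Confirm that Appendix A schedules creatinine during treatment. If it does not, add the test at the existing Month 3 and Month 5 draws; otherwise the limit acts only on values obtained in routine care. Those two draws would leave Months 5 to 7 unchecked, because the Section 6 list for Month 7 has no blood draw.

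The cost is one phrase in an existing sentence and, if needed, one test at two existing draws. An occasional extra participant, each 1 of 60, would come off drug and, under the same sentence, leave the study. The sponsor could avoid that loss of data by stopping drug for this trigger while continuing pain logs and follow-up.
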